4.3.3. Adherence to Study Drug

The adherence to SC LEN, IV infusion TAB and/or ZAB will be assessed by adherence to the projected injection/infusion interval, which is 26 weeks (182 days) between 2 adjacent injection/infusion visits. The number of days from the projected injection/infusion visit date will be calculated for each injection/infusion visit (excluding the 1st injection visit) as the injection/infusion visit date minus the previous injection/infusion visit date plus 1 day minus 182 days. The number of days from the projected injection visit date will be classified into the following categories:

- < - 14 days
- -14 to -8 days
- -7 to -3 days
- \pm 2 days
- 3 to 7 days
- 8 to 14 days
- > 14 days

The number and percentage of participants in each category will be summarized for treatment group 1 for the injection/infusion visits of interest.

4.4. Study Duration in the Randomized Phase

Due to long-acting feature of the study drug, study duration in randomized phase will be summarized by treatment group using the Safety Analysis set.

Study duration in randomized phase is calculated as the last study date in randomized phase (Section 3.8.1) minus Study Day 1 (Randomized Phase) plus 1.

For the calculation of the study duration, the data cut date will be used to impute the last study date in randomized phase for subjects who have not permanently discontinued study at the time of the data cut date.

Study duration will be expressed in days and will be summarized using descriptive statistics and using the number and percentage of participants that stayed through the following applicable time periods: ≥ 1 day, ≥ 2 days, ≥ 8 days, ≥ 15 days, ≥ 4 weeks (28 days), ≥ 12 weeks (84 days), ≥ 24 weeks (168 days), ≥ 26 weeks (182 days), ≥ 38 weeks (266 days), ≥ 50 weeks (350 days), ≥ 52 weeks (364 days), etc.

4.5. Protocol Deviations

Participants who did not meet the eligibility criteria for study entry, but enrolled in the study will be summarized regardless of whether they were exempted by the sponsor or not. The summary will present the number and percentage of participants who did not meet at least 1 eligibility criterion and the number of participants who did not meet specific criteria by treatment group based on the Safety Analysis Set. A by-participant listing will be provided for those participants who did not meet at least 1 eligibility (inclusion or exclusion) criterion. The listing will present the eligibility criterion (or criteria if more than 1 deviation) that participants did not meet and related comments, if collected.

Protocol deviations occurring after participants entered the study are documented during routine monitoring. The number and percentage of participants with important protocol deviations and number of important protocol deviations by deviation category (eg, eligibility criteria, informed consent) will be summarized by treatment group for the Safety Analysis Set. A by-participant listing will be provided for those participants with important protocol deviation.

5. BASELINE CHARACTERISTICS

5.1. Demographics and Baseline Characteristics

Participant demographic variables (ie, age, sex at birth, gender identity, sexual orientation, race, region and ethnicity) and baseline characteristics (body weight [in kg], height [in cm], body mass index [BMI; in kg/m²]) will be summarized by treatment group and overall using descriptive statistics for continuous variables and using number and percentage of participants for categorical variables. The summary of demographic data will be provided for the Safety Analysis Set.

A by-participant demographic and baseline characteristic listing, including the informed consent date, will be provided by participant ID number in ascending order.

5.2. Other Baseline Characteristics

The following baseline disease characteristics will be summarized by treatment group and overall using descriptive statistics for participants in the Safety Analysis Set:

- HIV-1 RNA categories (copies/mL): (a) < 50, (b) ≥ 50
- CD4 cell counts (/uL)
- CD4 cell counts categories (/uL): (a) < 50, (b) ≥ 50 to < 200, (c) ≥ 200 to < 350, (d) ≥ 350 to < 500, and (e) ≥ 500
- CD4 percentage (%)
- Mode of infection (HIV risk factors)
- HIV disease status
- eGFR (mL/min/1.73m²)
- Baseline oral ARV regimen
- Duration of baseline oral ARV regimen

A by-participant listing of other baseline characteristics will be provided by participant ID number in ascending order.

5.3. Medical History

Medical history will be collected at screening. Medical history data will be coded and listed.

6. EFFICACY ANALYSES

Analysis of efficacy data for randomized phase will be conducted on the FAS, unless otherwise specified.

On-treatment data during randomized phase will be used for some efficacy analyses (eg. snapshot analysis) using FAS and all efficacy analyses using Per-Protocol analysis set. On-Treatment data during randomized phase include: 1)for treatment group 1: data collected up to the earliest date of (196 days [28 weeks] after the last dose date (randomized phase) of complete long acting regimen, date of restarting ART); 2)for treatment group 3: data collected up to 1 day after permanent discontinuation of study drug in the randomized phase.

6.1. Primary Efficacy Endpoint

6.1.1. Definition of the Primary Efficacy Endpoint

The primary efficacy endpoint of this study is the proportion of participants with HIV-1 RNA ≥ 50 copies/mL at Week 26 as defined by the FDA-defined snapshot algorithm {U. S. Department of Health and Human Services 2015}. The proportions are expressed as percentages for presentation purpose.

6.1.2. US FDA-Defined Snapshot Algorithm

The analysis window at Week 26 is defined as from Study Day 176 to Study Day 224, inclusive for treatment group 1 and Study Day 134 to Study Day 224, inclusive for treatment group 3. All HIV-1 RNA data collected on-treatment during the randomized phase will be used in the US FDA-defined snapshot algorithm. Virologic outcome will be defined as the following categories:

- **HIV-1 RNA < 50 copies/mL:** this includes participants who have the last available on-treatment HIV-1 RNA < 50 copies/mL in the Week 26 analysis window
- **HIV-1 RNA ≥ 50 copies/mL:** this includes participants
 - a) Who have the last available on-treatment HIV-1 RNA ≥ 50 copies/mL in the Week 26 analysis window, or
 - b) Who do not have on-treatment HIV-1 RNA data in the Week 26 analysis window and
 - Who discontinue study drug prior to or in the Week 26 analysis window due to lack of efficacy, or
 - Who discontinue study drug prior to or in the Week 26 analysis window due to AE or death and have the last available on-treatment HIV-1 RNA ≥ 50 copies/mL, or
 - Who discontinue study drug prior to or in the Week 26 analysis window due to reasons other than AE, death, or lack of efficacy and have the last available on-treatment HIV-1 RNA ≥ 50 copies/mL.

- **No Virologic Data in the Week 26 Window:** this includes participants who do not have on-treatment HIV-1 RNA data in the Week 26 analysis window because of the following:
 - Discontinuation of study drug prior to or in the Week 26 analysis window due to AE or death and the last available on-treatment HIV-1 RNA < 50 copies/mL, or
 - Discontinuation of study drug prior to or in the Week 26 analysis window due to reasons other than AE, death, or lack of efficacy and the last available on-treatment HIV-1 RNA < 50 copies/mL or,
 - Missing data during the window but on study drug.

The flowchart of the US FDA-defined snapshot algorithm is provided in Appendix 2.

The Week 26 virologic outcomes for the US FDA-defined snapshot algorithm will be listed.

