3.1.1. Randomized Phase

Treatment Group 1

Participants in Treatment Group 1 will receive the long-acting regimen consisting of LEN, GS-5423, and GS-2872.

Participants will discontinue their baseline oral ART following administration of the complete study drugs on Day 1 (SC LEN 927 mg, oral LEN 600 mg, and IV infusions of GS-5423 and GS-2872), and will self-administer oral LEN 600 mg at home on Day 2. Participants will also receive study drug (SC LEN and IV infusion of GS-5423 and GS-2872) at Week 26.

All participants in Treatment Group 1 will return to the study center for visits at Weeks 4, 12, 24, 26, 38, 50, and 52.

Treatment Group 3

Participants in Treatment Group 3 will continue their baseline oral ART through Week 52. After Day 1, participants in Treatment Group 3 will return to the study center for visits at Weeks 12, 26, 38, 50, and 52.

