1.2.1. Randomized Phase

Participants in Treatment Group 1 will receive the long-acting regimen consisting of LEN, GS-5423, and GS-2872.

Participants will discontinue their baseline oral ART following administration of the complete study drugs on Day 1 (SC LEN 927 mg, oral LEN 600 mg, and IV infusions of GS-5423 and GS-2872), and will self-administer oral LEN 600 mg at home on Day 2. Participants will also receive study drug (SC LEN and IV infusion of GS-5423 and GS-2872) at Week 26.

All participants in Treatment Group 1 will return to the study center for visits at Weeks 4, 12, 24, 26, 38, 50, and 52.

Participants in Treatment Group 3 will continue their baseline oral ART through Week 52. After Day 1, participants in Treatment Group 3 will return to the study center for visits at Weeks 12, 26, 38, 50, and 52.

Duration of treatment in the Randomized Phase is 52 weeks.

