3.8.2. Analysis Visit Windows

Participant visits might not occur on protocol-specified days. Therefore, for the purpose of analysis, observations will be assigned to analysis windows.

The analysis windows for HIV-1 RNA, CD4+ cell count, CD4 %, Hematology, Chemistry, Lipid Panel, Urinalysis, Urine Chemistry, Urine Pregnancy Laboratory Tests, Vital Signs, Weight and ECG are provided in Table 3-2 to Table 3-5.

Table 3-2. Analysis Visit Windows for HIV-1 RNA

Analysis Visit	Randomized Phase					
	LEN + GS-5423 + GS-2872 Group (Treatment Group 1)			SBR Group (Treatment Group 3)		
	Nominal Study Day	Visit Window Study Day		Nominal Study Day	Visit Window Study Day	
		Lower Limit	Upper Limit		Lower Limit	Upper Limit
Baseline			1			1
Week 4	28	2	56	NA	NA	NA
Week 12	84	57	126	84	2	133
Week 24	168	127	175	NA	NA	NA
Week 26	182	176	224	182	134	224
Week 38	266	225	308	266	225	308
Week 50	350	309	357	350	309	357
Week 52	364	358	Min (406, Study Day 1 (Extension Phase))	364	358	Min (406, Study Day 1 (Extension Phase))

NA = Not applicable

For participants who entered extension phase, data after study day 1 (extension phase) are categorized under Analysis visit “Extension”; for participants who did not enter extension phase, data after the upper limit of Week 52 are categorized under “Post-Week 52”.

Table 3-3. Analysis Visit Windows for Chemistry, Hematology, Urinalysis

Analysis Visit	Treatment Group 1			Treatment Group 3		
	Nominal Study Day	Visit Window Study Day		Nominal Study Day	Visit Window Study Day	
		Lower Limit	Upper Limit		Lower Limit	Upper Limit
Baseline			1			1
Week 4	28	2	56	NA	NA	NA
Week 12	84	57	133	84	2	133
Week 26	182	134	224	182	134	224
Week 38	266	225	315	266	225	315
Week 52	364	316	Min (413, Study Day 1 (Extension Phase))	364	316	Min (413, Study Day 1 (Extension Phase))

For participants who entered extension phase, data after study day 1 (extension phase) are categorized under Analysis visit “Extension”; for participants who did not enter extension phase, data after the upper limit of Week 52 are categorized under “Post-Week 52”.

Table 3-4. Analysis Visit Windows for Vital Signs, and Weight

Analysis Visit	Treatment Group 1			Treatment Group 3		
	Nominal Study Day	Visit Window Study Day		Nominal Study Day	Visit Window Study Day	
		Lower Limit	Upper Limit		Lower Limit	Upper Limit
Baseline			\leq First Dose Date, if time not available \leq First Dose Date/Time, if time available			1
Day 1 (0.5 h Postdose)	1	> First Dose Date/Time	1	NA	NA	NA

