6.2.2. Analysis of the Secondary Efficacy Endpoints

6.2.2.1. Analysis of the Proportion of Participants with HIV-1 RNA \geq 50 copies/mL at Week 52 as Determined by US FDA-defined Snapshot Algorithm

The proportion of participants with HIV-1 RNA \geq 50 copies/mL at Week 52 as determined by US FDA-defined snapshot algorithm will be analyzed similarly to the primary efficacy endpoint.

For both treatment group 1 and 3, the analysis window at Week 52 is defined as from Study Day 358 to Study 406 if a participant did not enter the extension phase, or to Study Day 1 (extension phase) if a patient entered the extension phase.

The analyses for the above endpoint will be conducted using the FAS and the Week 52 PP analysis set, respectively.

6.2.2.2. Analysis of the Proportion of Participants with HIV-1 RNA $<$ 50 copies/mL at Weeks 26 and 52 as Determined by US FDA-defined Snapshot Algorithm

The proportion of participants with HIV-1 RNA $<$ 50 copies/mL at Weeks 26 and 52 as determined by US FDA-defined snapshot algorithm will be analyzed similarly to the primary efficacy endpoint, and be conducted using the FAS and the PP analysis set correspondingly.

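### The Week 26 snapshot window opens 42 days earlier in Group 3 than in Group 1, so the same suppressed early leaver is a success in control and has no virologic data in Group 1

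*SAP*

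**What the plan says.** SAP 6.1.2 defines the Week 26 snapshot window as "Study Day 176 to Study Day 224, inclusive for treatment group 1 and Study Day 134 to Study Day 224". SAP Table 3-2 gives the same limits. They follow the visit lists. For Group 1, SAP 1.2.1 states: "All participants in Treatment Group 1 will return to the study center for visits at Weeks 4, 12, 24, 26, 38, 50, and 52". For the other arm, Protocol 3.1.1 states: "participants in Treatment Group 3 will return to the study center for visits at Weeks 12, 26, 38, 50, and 52". Group 3 therefore has nothing scheduled between Week 12 and Week 26.

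Under SAP 6.1.2 the success category covers "participants who have the last available on-treatment HIV-1 RNA < 50 copies/mL in the Week 26 analysis window". A participant with no on-treatment value in the window falls under no virologic data by several routes. One is "Discontinuation of study drug prior to or in the Week 26 analysis window due to reasons other than AE, death, or lack of efficacy", provided that the last on-treatment value was below 50. The route for AE or death carries the same condition.

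On-treatment data in Group 1 end at the earliest of "196 days [28 weeks] after the last dose date (randomized phase) of complete long acting regimen, date of restarting ART" (SAP 6). In Group 3 they end 1 day after baseline ART is permanently stopped. SAP Table 3-1 removes from the Week 26 per-protocol set anyone without an on-treatment value in the window, unless the stop was for lack of efficacy.

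SAP 6.1.2 gives no reason for unequal windows, and the SAP describes no analysis with a common window.

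**The concern.** Windows that run without gaps from visit to visit suit by-visit tables. The snapshot has another purpose: it compares the arms, and its categories should mean the same thing in both. Here the arm decides how an identical history is classified if the last on-treatment value falls in Days 134–175.

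The history is realistic. Protocol 6.3.11.1 has Group 1 leavers resume baseline ART after the early-discontinuation visit, and that restart closes on-treatment data. A Group 1 leaver who restarts before Day 176 cannot supply a value in the window. A control leaver sampled on the same study day can.

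At stake is the Week 26 comparison of RNA < 50, a named secondary endpoint in a study meant to inform Phase 3 planning. Dropout at equal rates could look like a deficit for the new regimen. The per-protocol analysis cannot serve as a check, because the same rule keeps the control leaver and removes the Group 1 leaver.

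**Working it through.** **Windows (SAP 6.1.2, Table 3-2).**
- Group 1 cut between Weeks 24 and 26: (168 + 182)/2 = 175, so the window starts at Day 176. Length: 224 − 176 + 1 = 49 days.
- Group 3 cut between Weeks 12 and 26: (84 + 182)/2 = 133, so the window starts at Day 134. Length: 224 − 134 + 1 = 91 days.
- Difference in start: 176 − 134 = 42 days.
- On-schedule Week 26 visit (Protocol Tables 1 and 2, ± 6 days): 182 ± 6 = Day 176–188, wholly inside the shorter window.

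**Histories classified under SAP 6.1.2.** In rows 1 to 3 the participant discontinues and has no later on-treatment sample.

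| Last on-treatment RNA, Days 134–175 | Group 1 | Group 3 |
|---|---|---|
| < 50, stops for a reason other than lack of efficacy | No virologic data; out of PP | < 50; in PP |
| < 50, stops for lack of efficacy | ≥ 50 | < 50 |
| ≥ 50, stops for any reason | ≥ 50 | ≥ 50 |
| ≥ 50, no later sample to Day 224, never recorded as discontinued | No virologic data | ≥ 50 |

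Row 1 is the point made here. Neither of its two outcomes counts as ≥ 50, so it leaves the primary endpoint alone.

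**Check of the interval method.** The plan (Protocol 8.11, SAP 1.3) says that with 50 versus 25 participants the 95% CI excludes 0 from 8 Group 1 failures against 0 control failures, and from 12 against 1. I used the exact unconditional one-sided p-value at a difference of 0, maximised over the common proportion, with the score statistic named in the SAP's SAS code, and compared it with 0.025:
- control 0/25: p = 0.0403 at 7 failures, 0.0239 at 8;
- control 1/25: p = 0.0403 at 11 failures, 0.0239 at 12.

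Both thresholds reproduce.

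**Size on the < 50 endpoint.** Assumptions: planned sizes of 50 and 25; 1 and 0 participants with RNA ≥ 50 at Week 26, the counts reported in Protocol 1.4.1.2; no other missing data; assumed numbers of row 1 leavers, because the documents give none.
- Each Group 1 leaver costs that arm 1/50 = 2.0 points.
- Each Group 3 leaver costs that arm 0 under the SAP windows, but 1/25 = 4.0 points with a common Day 176 start.

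Difference in % < 50, Group 1 minus Group 3 (exact 95% CI):

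| Leavers, Group 1 / Group 3 | SAP windows | Common Day 176 start |
|---|---|---|
| 0 / 0 | −2.0 (−11.1 to 12.3) | −2.0 (−11.1 to 12.3) |
| 1 / 1 | 48/50 − 25/25 = −4.0 (−13.9 to 10.7) | 48/50 − 24/25 = 0.0 (−11.0 to 16.9) |
| 2 / 1 (4% each) | 47/50 − 25/25 = −6.0 (−16.9 to 8.4) | 47/50 − 24/25 = −2.0 (−13.6 to 14.9) |
| 4 / 2 (8% each) | 45/50 − 25/25 = −10.0 (−22.0 to 5.5) | 45/50 − 23/25 = −2.0 (−15.7 to 16.9) |

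With equal dropout rates the common window returns the no-dropout difference of −2.0, while the SAP windows give −6.0 and −10.0. The primary endpoint stays at 1/50 versus 0/25, +2.0 (−12.3 to 11.1), in every row.

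**The case against.** The best defence is that the SAP applies one rule consistently. Limits are midpoints between scheduled visits, and the arms have different schedules. Reach is also small: in Days 134–175 Group 3 can contribute only early-discontinuation, unscheduled or off-window samples, and only up to 1 day after ART stops. A Group 1 participant who stops without restarting ART can still supply on-treatment data to Day 1 + 196 = Day 197, inside the window. The study is not powered for comparison. All of this stands and limits the size. It does not justify using by-visit limits in a between-arm classification.

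A reader might infer more in three places.

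- **That the primary comparison is distorted by participants with RNA ≥ 50 before Day 176 and no Week 26 sample.** This mostly fails. SAP Appendix 2 dates a Group 1 discontinuation no later than 196 days after the last complete dose. With only the Day 1 dose that is Day 197, inside the window, so a last value ≥ 50 is a failure in both arms. No virologic data survives only if discontinuation is never recorded and no sample is taken through Day 224. Protocol 1.4.1.2 also reports no control participant with RNA ≥ 50 at Week 26, so the wider window created no control failure.
- **That Week 52 shows the sponsor preferring equal windows.** SAP 6.2.2.1 does say "For both treatment group 1 and 3, the analysis window at Week 52 is defined as from Study Day 358", but both arms have a Week 50 visit, so the midpoint rule gives the same day.
- **That the unequal Week 12 windows in Table 3-2 raise the same problem.** The Week 12 snapshot serves only the DMC futility review. Its details are left to the DMC charter, and the SAP's text there is partly redacted.

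**Conclusion.** The point holds for the secondary Week 26 endpoint of RNA < 50 and for membership of the Week 26 per-protocol set. The direction is towards control. The size is 4 points on the control proportion per affected control participant, taking the planned 25 as denominator. How many there are is unknown: the figures for one to four leavers per arm rest on assumed counts, and the true number may be zero.

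It should not be read as a flaw in the primary result. Ordinary leavers do not move the ≥ 50 endpoint. It could move only in rare cases and in opposite directions: a lack-of-efficacy stop with last RNA < 50 in Days 134–175 counts against Group 1 alone, and the undocumented-discontinuation case counts against Group 3 alone.

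**What to change.** Add to the SAP a labelled Week 26 snapshot analysis with Day 176–224 in both arms, for both the < 50 and ≥ 50 proportions, on the FAS and on a per-protocol set rederived with that window. Report by arm how many participants change category. If none do, one sentence closes the matter.

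It should be an additional analysis and not a new definition of the primary window, because SAP 2.2 records the Week 26 primary analysis as already conducted and as final for that endpoint. Table 3-2 can stay as it is for the by-visit missing-equals-failure and missing-equals-excluded tables.

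The cost is a short SAP paragraph and one table rerun. An early off-schedule control sample may move its participant to no virologic data. No on-schedule Week 26 visit (Day 176–188) is lost.

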6.1.3. Analysis of the Primary Efficacy Endpoint

The Primary analysis of the proportion of participants with HIV-1 RNA ≥ 50 copies/mL as determined by the US FDA-defined snapshot algorithm at Week 26 will be based on the FAS. The 95% CI of the proportion of participants with HIV-1 RNA ≥ 50 copies/mL for each treatment group will be provided using the Clopper-Pearson Exact method. The point estimate of treatment difference in the percentage of participants with HIV-1 RNA ≥ 50 copies/mL and the associated 2-sided 95% CI will be constructed based on an unconditional exact method using 2 inverted 1-sided tests {Chan 1999}.

The Fisher's exact test will also be used to compare the percentages of participants between treatment groups. A secondary analysis based on the Week 26 PP analysis set will also be performed.

6.2. Secondary Efficacy Endpoints

6.2.1. Definition of the Secondary Efficacy Endpoints

The secondary efficacy endpoints of this study are:

- Proportion of participants with HIV-1 RNA ≥ 50 copies/mL at Week 52 as determined by the US FDA-defined snapshot algorithm
- Proportion of participants with HIV-1 RNA < 50 copies/mL at Weeks 26 and 52 as determined by the FDA-defined snapshot algorithm
- Change from baseline in CD4+ T-cell counts at Weeks 26 and 52

6.2.2. Analysis of the Secondary Efficacy Endpoints

6.2.2.1. Analysis of the Proportion of Participants with HIV-1 RNA \geq 50 copies/mL at Week 52 as Determined by US FDA-defined Snapshot Algorithm

The proportion of participants with HIV-1 RNA \geq 50 copies/mL at Week 52 as determined by US FDA-defined snapshot algorithm will be analyzed similarly to the primary efficacy endpoint.

For both treatment group 1 and 3, the analysis window at Week 52 is defined as from Study Day 358 to Study 406 if a participant did not enter the extension phase, or to Study Day 1 (extension phase) if a patient entered the extension phase.

The analyses for the above endpoint will be conducted using the FAS and the Week 52 PP analysis set, respectively.

6.2.2.2. Analysis of the Proportion of Participants with HIV-1 RNA $<$ 50 copies/mL at Weeks 26 and 52 as Determined by US FDA-defined Snapshot Algorithm

The proportion of participants with HIV-1 RNA $<$ 50 copies/mL at Weeks 26 and 52 as determined by US FDA-defined snapshot algorithm will be analyzed similarly to the primary efficacy endpoint, and be conducted using the FAS and the PP analysis set correspondingly.

